**End of Treatment (EOT)**

Procedures and evaluations for the end of treatment visit should be performed 28 days ( $\pm 7$  days) after the last dose of ACE-536.

**Post Treatment Follow-Up (PTFU)**

Procedures and evaluations for the post treatment follow-up visit should be performed 2 months ( $\pm 7$  days) after the last dose of ACE-536.

**Long-Term Follow-Up (LTFU)**

LTFU visits should occur every 3 months ( $\pm 7$  days) for 3 years after the last dose of ACE-536.

**End of Study (EOS)**

Procedures and evaluations for the end of study visit should be performed approximately 3 years after the last dose of ACE-536).

- Patients who discontinue treatment early should complete the EOS visit approximately 3 years after the EOT visit.
- If a patient has a positive ADA result at the last visit, the patient may be asked to return for additional ADA testing every three months until a negative result is obtained or the result is considered to be stabilized.

## **5.2. General Considerations**

Unless otherwise noted, continuous data will be summarized with the following descriptive statistics: number of observations (n), mean, standard deviation (STD), median, minimum and maximum. Categorical data will be summarized with frequencies (n) and percentages (%). In cases where missing data cause percentages not to sum to 100, a missing data row will be provided. Percentages will use column totals as the denominator unless otherwise indicated. For time to event variables, the Kaplan-Meier curves will be presented if the number of patients is more than 5.

All study data will be included in study data listings. Missing data will generally not be imputed, unless otherwise stated.

Data summaries may also be presented for LTB and HTB patients separately as specified. All summaries will be descriptive. No formal hypothesis testing is planned.

### **5.3. Disposition of Patients**

The number and percentage of patients receiving study treatment who completed the treatment period and study period along with the associated reasons for discontinuation from treatment and/or withdrawal from study will be presented.

### **5.4. Demographic, Baseline Characteristics, and Disease History**

The following baseline and demographic characteristics will be summarized by descriptive statistics for the ITT population:

- Race, ethnicity, age, sex, height, weight
- Prior MDS Therapies, time from diagnosis; Prior erythropoiesis stimulating agents (ESA); IPSS and IPSS-R risk group; WHO Subtypes; ICT use
- Baseline ECOG performance status
- Baseline transfusion status (LTB or HTB)
- Baseline hemoglobin and baseline transfusion burden
- Baseline erythropoietin (EPO) and baseline serum ferritin
- RS and SF3B1 mutation status; any splicing factor (yes or no)
- Baseline bone marrow blasts

Demographic and baseline data, medical history, and disease history data will also be listed for each patient.

### **5.5. Medical History**

Medical history will be coded using MedDRA Version 20.0. Summary of medical history will be tabulated by system organ class (SOC) alone and by both SOC and the preferred term (PT).

### **5.6. Study Drug Exposure**

Study drug exposure will be descriptively summarized for the safety population and will present the duration of exposure, the number of treatment cycles, the total dose administered, the number of patients with dose delay and reduction, and the number of patients with dose increase.

The duration of exposure will be calculated as (last dose date – first dose date) + 21.

The total number of cycles will be summarized by presenting the number and percentage of patients in each category.

The total dose administered is the total amount of study drug in mg a patient received during the treatment period.

Study drug administration details will be listed for each patient.

## 5.7. Prior and Concomitant Medication and Procedures

### 5.7.1. Prior and Concomitant Medication

The prior and concomitant medications are coded with WhoDrugDDEB2 201209. The medications will be presented for the safety population.

Medications will be assigned as prior or concomitant based on the following rules:

- If both the start and stop date exist and are before the first dose date of study drug, the medication will be counted as prior.
- If the start date is on or after the first dose date of study drug, the medication will be counted as concomitant.
- If the start date is before the first dose date of study drug and the stop date is after the first dose date of study drug or the medication is ongoing, the medication will be counted as prior and concomitant.
- If the start date is missing and the stop date is before the first dose of study drug, the medication will be counted as prior.
- If the start date is missing and the stop date is after the first dose of study drug or the medication is ongoing, the medication will be counted as concomitant.
- If the start and stop dates are missing, the medication will be counted as concomitant.

Prior and concomitant medications will be summarized separately.

### 5.7.2. Non-Medication Procedures

All non-medication procedures will be listed for each patient.

## 5.8. Efficacy and Safety Analyses

No formal hypothesis testing is planned. All efficacy analyses will be performed using the ITT population.

In general, the below rules apply to the derivations of efficacy endpoints related to hemoglobin and RBC transfusion data unless specified otherwise:

- Hemoglobin measurements within 7 days following RBC transfusion will be excluded from the efficacy analysis
- For each patient, all efficacy endpoints will be derived based on an analysis cutoff day, defined as the last dose + 56 days or the last date from transfusion record data, whichever is earlier.

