10.2.1. Other Treatments for MDS

If treatment with azacitidine, decitabine, lenalidomide, ESA, or G-CSF is required during the ACE-536 treatment period, the patient should be discontinued from treatment with study drug and complete the EOT visit and enter the follow-up period. Iron chelation therapy is allowed for patients without treatment interruption. For patients with treatment interruption, iron chelation therapy is allowed unless initiated within 56 days prior to C1D1. If iron chelation therapy is required during study treatment, patient should follow standard of care for management of iron chelation therapy.

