#### 5.8.2.2. RBC Transfusion Independence

For patients with  $\geq 2$  units of RBC transfusion at baseline, RBC transfusion independence (RBC-TI) response is defined as not requiring RBC transfusion for 8 or more weeks while on treatment.

The proportion of RBC-TI responders will be estimated by a point estimate along with the exact 95% confidence interval based on binomial distribution. The denominator is the number of patients with  $\geq 2$  units of RBC transfusion at baseline.

Time to RBC-TI will be defined as the time from the first dose date to the starting date of the first consecutive 8-week interval not requiring RBC transfusion. Duration of RBC-TI will be calculated as the longest period of time not requiring RBC transfusion during treatment and will be censored at the analysis cutoff date for ongoing responses.

Both time to and duration of RBC-TI will be analyzed as continuous variables and summarized by descriptive statistics for RBC-TI responders only. Duration of RBC-TI will also be analyzed as a time to event variable using Kaplan-Meier method.

The derivations of RBC-TI response, time to and duration of RBC-TI will be listed for each patient.

RBC-TI responders may experience multiple periods of  $\geq 8$  weeks of RBC-TI response. For all RBC-TI responders, the number of episodes and cumulative duration will be summarized. As an exploratory analysis, the cumulative duration of the multiple responses will be analyzed using Kaplan-Meier method.

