#### 5.8.2.3. HI-E Response Rate

Erythroid (HI-E) response will be defined following IWG 2006 criteria.

- For low transfusion burden (LTB) patients, a hemoglobin increase of  $\geq 1.5$  g/dL from baseline during any rolling 8-week period in the absence of transfusion. The rolling 8-week period starts and ends at a hemoglobin measurement date with duration  $\geq 8$  weeks.

- For high transfusion burden (HTB) patients, a reduction by  $\geq 4$  RBC units transfused during any rolling 8-week interval on treatment compared to baseline.

A point estimate of the proportion of HI-E responders will be presented along with its associated exact 95% confidence interval based on binomial distribution. HI-E response will also be listed for each patient.

There are two versions of a HI-E response for LTB patients.

- All hemoglobin values increase of  $\geq 1.5$  g/dL from baseline during any rolling 8-week period in the absence of transfusion.
- Mean hemoglobin value increase of  $\geq 1.5$  g/dL from baseline during any rolling 8-week period in the absence of transfusion.

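### The efficacy cutoff does not stop when another MDS therapy starts, and one of its two limbs is undefined

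*SAP*

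**What the plan says.** SAP 5.8 sets one analysis cutoff day per patient, "defined as the last dose + 56 days or the last date from transfusion record data, whichever is earlier". Its scope is general: "the below rules apply to the derivations of efficacy endpoints related to hemoglobin and RBC transfusion data unless specified otherwise". Modified HI-E, HI-E, RBC-TI and the duration analyses all depend on it.

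The related provisions are these:

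- SAP 5.8.2.2 defines RBC-TI as "not requiring RBC transfusion for 8 or more weeks while on treatment". SAP 5.8.2.3 counts, for HTB patients, "RBC units transfused during any rolling 8-week interval on treatment compared to baseline". Neither says how many days after the last dose still count as on treatment.
- Duration of RBC-TI is the longest transfusion-free period "during treatment and will be censored at the analysis cutoff date for ongoing responses". SAP 5.8.2.5 censors ongoing HI-E at the same cutoff.
- SAP 5.6 counts drug exposure as ending 21 days after the last dose.
- Protocol 10.2.1 begins "If treatment with azacitidine, decitabine, lenalidomide, ESA, or G-CSF is required during the ACE-536 treatment period" and directs that such patients stop study drug, have the EOT visit and enter follow-up. The Schedule of Events collects hematology and transfusion frequency at both EOT and PTFU.
- No section ends efficacy follow-up at the start of such a therapy. SAP 5.11 allows data to be excluded after a review of deviations, and SAP 5.11.1 lists unauthorized concomitant therapy as a violation.

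**The concern.** The therapies named in Protocol 10.2.1 as reasons to stop study drug include agents that can themselves raise hemoglobin or reduce transfusions. Once the patient is off ACE-536, nothing delays their start until day 56. If the cutoff ignores that start, a transfusion-free stretch or hemoglobin rise produced by the second agent is reported as a response to ACE-536, or lengthens one. SAP 5.11 is not an adequate guard. It is discretionary, and a therapy begun after the discontinuation that the protocol itself directs is not clearly a violation.

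The second issue is what the transfusion-record limb means. It could be the date of the last transfusion, or the last date on which transfusion data were collected. The two readings give opposite response status for the patients who do best.

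**Working it through.** The documents state no sample size, power or target rate, so there is no planned figure to reproduce. The checks are day arithmetic, worked patients and a small simulation.

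**Inputs.** Cutoff: last dose + 56 days (SAP 5.8). Response window: 8 weeks = 56 days (SAP 5.8.2.2, 5.8.2.3). Dosing interval: 21 days (Protocol 9.1). Exposure end: last dose + 21 days (SAP 5.6). PTFU: 2 months ± 7 days after the last dose (Schedule of Events), which is about days 54 to 68 if 2 months is taken as 61 days. Half-life: 14.9 to 16.2 days after a first dose in healthy women (Protocol 7.3).

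**1. New therapy.** Let the last dose be day L and another listed therapy start on day L + s. If transfusion status is known to PTFU, the last-collection reading gives a cutoff at or close to L + 56. The days credited under the other therapy are then up to 56 − s. As an assumed example, take s = 14 and no transfusion from L to L + 56.
- As written: the stretch is 56 days and counts as a full RBC-TI response, with 56 − 14 = 42 days under the other therapy.
- With a stop at new therapy: the stretch after the last dose is 14 days and earns no response by itself.
- A patient already responding would gain the same 42 days of duration.

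**2. The tail itself.** Of the 56 days, 21 are the normal dosing interval. The rest is 56 − 21 = 35 days, or 35/56 = 62.5%. Concentration at day 56 relative to day 21 is 2^(−35/14.9) = 0.20 to 2^(−35/16.2) = 0.22.

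**3. Effect of the 35 days on the RBC-TI rate.** The simulation used 20,000 patients per cell, assuming no drug effect, Poisson transfusion events and doses every 21 days. It does not model new therapy or A536-03 data.

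| Doses | Events per 8 weeks | Cutoff + 21 days | Cutoff + 56 days |
|---|---|---|---|
| 1 | 1 / 2 / 3 | 0 / 0 / 0% | 37.1 / 13.6 / 4.9% |
| 4 | 1 / 2 / 3 | 54.8 / 27.3 / 12.5% | 76.5 / 43.6 / 21.8% |
| 17 | 1 / 2 / 3 | 99.7 / 89.8 / 63.0% | 99.8 / 92.2 / 66.4% |

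The one-dose row agrees with the exact values e^(−1) = 36.8%, e^(−2) = 13.5% and e^(−3) = 5.0%. A full window needs one dose under + 56 days. Under + 21 days it needs three: (3 − 1) × 21 + 21 = 63 ≥ 56, whereas two doses give 42.

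**4. The undefined limb.** Day 0 is the first dose.

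| Patient | Last-transfusion reading | Last-collection reading |
|---|---|---|
| Last transfused day −10, then none; 87 doses | Cutoff day −10; no follow-up | Cutoff 86 × 21 + 56 = day 1862; responder |
| Transfused days 20 and 40, then none; 17 doses | Cutoff day 40; longest gap 20 days; non-responder | Cutoff 16 × 21 + 56 = day 392; gap 392 − 40 = 352 days; responder |
| No transfusion on record; 17 doses | This limb gives no date | Cutoff day 392 |

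The third case matters for hemoglobin endpoints too, because LTB means fewer than 4 units and includes zero.

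**The case against.** Four stronger readings are tempting, and the documents do not support them.

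- **That the plan truncates responders.** This needs the last-transfusion reading. The mention of transfusion records in SAP 5.8.2.1 makes that reading possible, but the censoring of ongoing RBC-TI points away from it. If the cutoff were the last transfusion, no transfusion-free spell could be ongoing there, and the censoring rule would apply only when a later transfusion is recorded after last dose + 56 days. Transfusions are also evaluated at each cycle, EOT and PTFU. This is an ambiguity, not a shown truncation.
- **That one rule does both harms at once.** Because the earlier date applies, the harms belong mostly to opposite readings. A last-transfusion cutoff removes the ongoing off-drug stretch; a last-collection cutoff spares the responders.
- **That all 56 days are off drug.** The first 21 are an ordinary dosing interval. A window lying wholly after the last dose is an edge case, starting on the last-dose day itself. For HI-E in LTB patients it is nearly excluded, since the period must begin and end on hemoglobin measurement dates.
- **That 56 days contradicts the 21 days in SAP 5.6.** The latter is an exposure measure, not a definition of on-treatment efficacy. AE reporting also runs to about 2 months after the last dose, so a tail fits the plan. The half-life describes concentration; the documents give no time course for loss of erythroid effect.

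It can also be said that the on-treatment wording already overrides the general rule. That is partial protection at best: the term has no numeric meaning, and the censoring of RBC-TI duration at the cutoff suggests that the tail is included. None of these arguments supplies a stop at new therapy.

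**Conclusion.** The point holds in this form. The firm finding is the missing stop at the start of another MDS therapy: followed as written, the rule can credit ACE-536 with up to 56 days of response or duration obtained under a different active agent. The documents do not say how many patients would start one within that time, so the effect on the reported rates cannot be computed. The second finding is an undefined term that should be settled in writing, since a literal coding would reverse response status in the examples above.

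The consequences are limited. The primary objective is safety, there is no primary efficacy endpoint, and no test is planned. Under the no-effect assumptions, the 35 extra days raise the RBC-TI rate by 9.3 to 21.7 points after 4 doses, but by only 0.1 to 3.4 points after 17. Direct-rollover patients also contribute A536-03 data, so the effect on response rates falls mainly on patients with treatment interruption who stop early. For others the tail mainly adds up to 35 days of duration.

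**What to change.** In SAP 5.8, define the cutoff as the earliest of:

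1. last dose + 56 days;
2. the start of any therapy that Protocol 10.2.1 names as requiring study drug to stop (iron chelation, which that section allows, is not included);
3. death or withdrawal from the study;
4. the last date on which transfusion status was ascertained, meaning a visit or contact and not the last transfusion.

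Item 4 also gives never-transfused patients a date. Because ongoing responses are censored at the cutoff, the SAP should state that items 2 and 3 then act as censoring dates in the Kaplan-Meier analyses of duration.

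Add a sensitivity analysis of RBC-TI, HI-E and their durations with the cutoff at last dose + 21 days. Requiring only that a responding window start by last dose + 21 days would not do the same job: any 56-day window that ends by last dose + 56 already starts on or before the last dose, so nothing would be excluded.

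The cost is a few lines of SAP text and derivation code. Concomitant medications are collected continuously, so start dates should be available. A few late responses, or some duration, may be lost.

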### 5.8.1. Primary Efficacy Endpoint

Since the primary objective of this study is to evaluate the long-term safety and tolerability of ACE-536 in patients with low or intermediate-1 risk MDS who were previously enrolled in study A536-03, there is no primary efficacy endpoint specified for this study.

### 5.8.2. Secondary Efficacy Endpoints

#### 5.8.2.1. Erythroid Response (modified HI-E from IWG 2006 criteria)

Erythroid response (modified HI-E from IWG 2006 criteria) is defined as the proportion of patients with:

- A mean hemoglobin (Hgb) increase  $\geq 1.5$  g/dL over an 8-week period as compared to baseline, not influenced by RBC transfusion, in LTB patients.
- A decrease of  $\geq 4$  units or  $\geq 50\%$  of units of RBCs transfused over a period of 8 weeks, relative to the 8 weeks immediately prior to Day 1, in HTB patients.

A point estimate of the proportion of patients achieving a modified erythroid response will be presented along with its associated exact 95% confidence interval based on binomial distribution.

The complete hemoglobin measurements and RBC transfusion records will be listed for each patient.

#### 5.8.2.2. RBC Transfusion Independence

For patients with  $\geq 2$  units of RBC transfusion at baseline, RBC transfusion independence (RBC-TI) response is defined as not requiring RBC transfusion for 8 or more weeks while on treatment.

The proportion of RBC-TI responders will be estimated by a point estimate along with the exact 95% confidence interval based on binomial distribution. The denominator is the number of patients with  $\geq 2$  units of RBC transfusion at baseline.

Time to RBC-TI will be defined as the time from the first dose date to the starting date of the first consecutive 8-week interval not requiring RBC transfusion. Duration of RBC-TI will be calculated as the longest period of time not requiring RBC transfusion during treatment and will be censored at the analysis cutoff date for ongoing responses.

Both time to and duration of RBC-TI will be analyzed as continuous variables and summarized by descriptive statistics for RBC-TI responders only. Duration of RBC-TI will also be analyzed as a time to event variable using Kaplan-Meier method.

The derivations of RBC-TI response, time to and duration of RBC-TI will be listed for each patient.

RBC-TI responders may experience multiple periods of  $\geq 8$  weeks of RBC-TI response. For all RBC-TI responders, the number of episodes and cumulative duration will be summarized. As an exploratory analysis, the cumulative duration of the multiple responses will be analyzed using Kaplan-Meier method.

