8.2. Secondary Objectives

- To evaluate erythroid response (modified HI-E from IWG 2006 criteria), defined as proportion of patients with:
 - A mean hemoglobin (Hgb) increase ≥ 1.5 g/dL over an 8-week period as compared to baseline, not influenced by RBC transfusion, in non-transfusion dependent (NTD) patients.
 - A decrease of ≥ 4 units or $\geq 50\%$ of units of RBCs transfused over a period of 8 weeks, relative to the 8 weeks immediately prior to Day 1, in transfusion dependent (TD) patients.
- To evaluate rates of erythroid, neutrophil and platelet (HI-E, HI-N and HI-P) responses (IWG 2006 criteria)
- To evaluate the rate of RBC transfusion independence lasting ≥ 8 weeks in TD patients
- To evaluate time to HI-E response and duration of HI-E response (modified and non-modified IWG 2006 criteria)
- To evaluate the mean change in RBC transfusion burden in TD patients and mean change in hemoglobin levels in NTD patients
- To evaluate the PK profile of ACE-536
- To evaluate other PD effects (e.g., iron overload/metabolism, EPO, and reticulocytes)

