15.2.3. Secondary Analysis

Efficacy/Pharmacodynamic Effects Analysis of Secondary Endpoints:

All efficacy analyses will be performed for the EE and mITT populations.

Efficacy will be evaluated by determining the proportion of patients who have a modified HI-E erythroid response rate based upon the IWG 2006 criteria ([Appendix 5](#)), defined as 1) A mean hemoglobin increase ≥ 1.5 g/dL over an 8-week period as compared to baseline, not influenced by RBC transfusion in NTD patients or 2) A decrease of ≥ 4 units or $\geq 50\%$ of units of RBCs transfused over a period of 8 weeks, relative to the number of units of RBCs transfused in the 8 weeks immediately prior to Cycle 1 Day 1 in TD patients.

Baseline hemoglobin will be the average of two or more measures (not influenced by RBC transfusion) performed during the screening period for study A536-03 (for patients without interruption) or study A536-05 (for patients with interruption).

Baseline units of RBCs transfused will be the 8-week period prior to study A536-03 (for patients without interruption) or study A536-05 (for patients with interruption).

The erythroid response will be summarized using both a point estimate and its exact 95% confidence interval based on binomial distribution.

No direct comparison testing with concurrent or historical controls will be performed.

Analysis of other secondary efficacy/pharmacodynamic endpoints will include:

- Time to HI-E response and duration of HI-E response as per the IWG 2006 criteria and modified IWG criteria.
- Mean RBC transfusion burden
- Rate of RBC transfusion-free period lasting \geq 8 weeks in TD patients.
- Mean hemoglobin level change in NTD patients
- Other PD endpoints including:
 - Biomarkers for iron overload/metabolism
 - Relationship of biomarkers to response
 - Rates of HI-E, HI-N and HI-P

Exploratory endpoints will include:

- Biomarkers related to the TGF β superfamily.
- Patient-reported quality of life using tools including but not limited to the FACT-An questionnaire.

All binary endpoints will be summarized using both a point estimate and its exact confidence interval based on the binomial distribution. The time-to-event type secondary endpoints will be analyzed using Kaplan-Meier method to estimate the survival curve and median time to event and 95% confidence interval.

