15.5. Deviation from Original Analysis Plan

A formal Statistical Analysis Plan (SAP) for the analysis and presentation of data from this study will be prepared before the database lock. Deviations from the statistical analyses outlined in this protocol will be indicated in this plan; any further modifications will be noted in the final clinical study report.

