## 2. STUDY OBJECTIVES

Primary Objective:

- To evaluate the long-term safety and tolerability of ACE-536 in patients with low or intermediate-1 risk MDS who were previously enrolled in study A536-03.

Secondary Objectives:

- To evaluate erythroid response (modified HI-E from International Working Group [IWG] 2006 criteria), defined as proportion of patients with:
  - A mean hemoglobin (Hgb) increase  $\geq 1.5$  g/dL over an 8-week period as compared to baseline, not influenced by red blood cell (RBC) transfusion, in non-transfusion dependent (LTB) patients (refer to [Section 5.1](#) for definitions of LTB and HTB).
  - A decrease of  $\geq 4$  units or  $\geq 50\%$  of units of RBCs transfused over a period of 8 weeks, relative to the 8 weeks immediately prior to Day 1, in transfusion dependent (HTB) patients.
- To evaluate rates of erythroid, neutrophil and platelet (HI-E, HI-N and HI-P) responses (IWG 2006 criteria)
- To evaluate the rate of RBC transfusion independence lasting  $\geq 8$  weeks in HTB patients
- To evaluate time to HI-E response and duration of HI-E response (modified and non-modified IWG 2006 criteria)
- To evaluate the mean change in RBC transfusion burden in HTB patients and mean change in hemoglobin levels in LTB patients
- To evaluate the pharmacokinetic (PK) profile of ACE-536
- To evaluate other pharmacodynamic (PD) effects (e.g., iron overload/metabolism, erythropoietin [EPO], and reticulocytes)

Exploratory Objectives:

- To examine biomarkers related to the TGF- $\beta$  superfamily

- To examine self-reported quality of life using tools including but not limited to the FACT-An questionnaire

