## 5. STATISTICAL METHODOLOGY

### 5.1. Definitions

#### Transfusion Status

For patients without treatment interruption, transfusion status (LTB or HTB) will carry-over from the base study A536-03. For patients with treatment interruption, transfusion status will be reassessed prior to C1D1 of study A536-05. Transfusion status for all patients is defined as follows for all patients:

- LTB patients are defined as patients who require a transfusion of < 4 units of RBCs in the 8 weeks prior to C1D1
- HTB patients are defined as patients who require a transfusion of  $\geq 4$  units of RBCs in the 8 weeks prior to C1D1

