**Baseline Transfusion Burden**

Baseline transfusion burden will be calculated as the total amount of RBC transfusion during the 8 weeks prior to Cycle 1 Day 1.

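### The SAP calculates the transfusion-independence rate in patients with at least 2 baseline units, but the objective is set for HTB patients (at least 4 units); SAP 5.13 does not declare this and no HTB rate is planned

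*SAP*

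**What the plan says.** Protocol 8.2 gives the secondary objective as "To evaluate the rate of RBC transfusion independence lasting ≥ 8 weeks in TD patients", and Protocol 15.2.3 lists the matching analysis as "Rate of RBC transfusion-free period lasting \geq 8 weeks in TD patients". The SAP restates the objective in Section 2 with its own term: "To evaluate the rate of RBC transfusion independence lasting $\geq 8$ weeks in HTB patients".

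SAP 5.1 fixes the groups: "HTB patients are defined as patients who require a transfusion of $\geq 4$ units of RBCs in the 8 weeks prior to C1D1", and "LTB patients are defined as patients who require a transfusion of < 4 units of RBCs in the 8 weeks prior to C1D1". It also defines baseline transfusion burden as the "total amount of RBC transfusion during the 8 weeks prior to Cycle 1 Day 1".

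SAP 5.8.2.2 defines RBC-TI response for patients with 2 or more units at baseline and says of the rate: "The denominator is the number of patients with $\geq 2$ units of RBC transfusion at baseline".

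On departures from the protocol's analyses, Protocol 15.5 says: "Deviations from the statistical analyses outlined in this protocol will be indicated in this plan". SAP 5.13 lists five changes: the NTD/TD terms, mITT, time to and duration of modified HI-E, the efficacy-evaluable population, and baseline hemoglobin.

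**The concern.** The objective and the analysis name different populations for the same secondary endpoint. A patient with 2 or 3 units in the 8 weeks before C1D1 is LTB by the SAP's own definition, yet counts in the denominator, and possibly in the numerator, of an endpoint that Section 2 restricts to HTB.

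The study is descriptive, so the point estimate and its interval are the whole result for this endpoint. Patients with a low baseline need go 8 weeks without a transfusion more easily than those with a high need, so adding them is likely to raise the rate. If the table is then read against the stated objective, it will be taken as the HTB rate. The HTB rate itself would have no planned estimate or interval.

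The point concerns the rate only. Time to and duration of RBC-TI are additions in the SAP, and no objective restricts them to HTB patients.

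**Working it through.** **1. Populations side by side**

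| Place | Population for the 8-week RBC-TI rate | Units in the 8 weeks before C1D1 |
|---|---|---|
| Protocol 8.2, 15.2.3 | TD | at least 4 |
| SAP 2 with 5.1 | HTB | at least 4 |
| SAP 5.8.2.2 | no group named | at least 2 |

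The look-back window does not explain the difference: transfusion status and baseline burden both use the 8 weeks before C1D1. The at-least-2-unit set is therefore HTB plus the LTB patients with 2–3 units.

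**2. Is the change declared, or an HTB rate planned elsewhere?**

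- SAP 5.13: none of the five rows mentions RBC-TI. The NTD/TD row changes terms only, and 5.1 keeps the cut-off at 4 units.
- SAP 5.2: separate LTB and HTB summaries are optional and depend on being specified. Section 5.8.2.2 specifies none.
- SAP 5.8.4: the subgroup list covers RS, SF3B1, splicing factor, EPO, marrow blasts, IPSS and IPSS-R. Transfusion status is not on it.

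**3. Size**

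The plan gives no counts, expected rates or sample-size calculation, so there is no figure to reproduce. Let s be the share of the at-least-2-unit set with 2–3 units, p1 their RBC-TI rate and p2 the HTB rate.

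Reported rate = s·p1 + (1 − s)·p2, so excess over the HTB rate = s × (p1 − p2).

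*Illustration; every input is assumed.* Renewal simulation with 60,000 patients per cell, 2-unit transfusions, a 50-week run-in and no drug effect. Patient rates are gamma-distributed (mean 3, 4.2 or 6 units per 8 weeks; shape 1, 2 or 4). Spacing is random (Poisson) or fairly regular (gamma gaps, shape 4). Patients are grouped by the observed count in the 8 weeks before day 1, so regression to the mean is included. The outcome is any transfusion-free gap of at least 8 weeks.

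Middle case (mean 4.2, shape 2), with s from 0.1 to 0.3:

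| Follow-up | Spacing | p1 | p2 | p1 − p2 | Excess (points) |
|---|---|---|---|---|---|
| 24 weeks | random | 74% | 45% | 29 | 2.9–8.7 |
| 24 weeks | regular | 67% | 16% | 51 | 5.1–15.3 |
| 52 weeks | random | 92% | 68% | 24 | 2.4–7.2 |
| 52 weeks | regular | 84% | 28% | 56 | 5.6–16.8 |
| 260 weeks | random | 100% | 92% | 8 | 0.8–2.4 |
| 260 weeks | regular | 97% | 49% | 48 | 4.8–14.4 |

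Range over all nine rate distributions, same s:

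| Follow-up | Random | Regular |
|---|---|---|
| 24–52 weeks | 0.7–13.3 | 3.7–20.5 |
| 104 weeks | 0.3–11.1 | 3.0–20.7 |
| 260 weeks | 0.0–8.2 | 2.0–19.7 |

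The excess was never negative. The 260-week rates also show that searching any 8-week window produces many chance responders, in HTB patients too. Changing the denominator does not remove that.

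**4. Precision cost of the HTB denominator**

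Assume 60 patients with at least 2 units and 50% response. With s = 0.1, HTB n = 60 × 0.9 = 54; with s = 0.3, n = 60 × 0.7 = 42. Exact (Clopper-Pearson) 95% intervals:

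- 30/60: 36.8–63.2% (26.4 points wide)
- 27/54: 36.1–63.9% (27.8 points wide)
- 21/42: 34.2–65.8% (31.6 points wide)

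**The case against.** The strongest reply is that nothing is hidden and little depends on it. SAP 5.8.2.2 states the 2-unit threshold twice, Protocol 15.5 requires deviations to be indicated in the SAP rather than in a particular table, and 5.13 covers only major changes. The primary objective is safety, all summaries are descriptive, and no sample size rests on this rate. Every HTB patient is inside the wider set, and RBC-TI derivations and baseline data are listed per patient, so the HTB rate can be rebuilt. The wider set also has a rationale: HI-E and modified HI-E are hemoglobin-based in LTB patients, so RBC-TI is the only response endpoint that captures transfusion benefit in those with 2–3 units.

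Much of this stands. It is a reason to keep the wider analysis, and it limits the seriousness. It does not remove the conflict: whatever 5.13 has to contain, 5.8.2.2 disagrees with the SAP's own Section 2. A new population for a named secondary endpoint is no smaller a change than replacing the label mITT by ITT, which is listed. A rate rebuilt by hand from listings is not a planned analysis.

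The size estimate is also open to attack. The 10–30% share is imposed, whereas the nine rate distributions imply shares of about 16–50%. Using each model's own share, the 24–52 week excess is about 3–13 points (random) and 6–27 (regular), so the imposed share does not exaggerate it. The absence of a drug effect is the more serious limit. Titration rules and the pre-transfusion threshold differ between TD and NTD patients and could narrow the gap, and the consistently non-negative excess follows largely from the model. If on-treatment response is equal in the two groups, the excess is zero.

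**Conclusion.** The concern holds. Followed as written, SAP 5.8.2.2 produces an RBC-TI rate for a population other than the one named in the protocol and in the SAP's own objective. SAP 5.13 does not record the change, and no section commits to the HTB rate. This rests on the text alone.

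The direction is probably upward. The size is unknown, because the documents give neither the share of patients with 2–3 units nor any response rates. The illustrative 1–13 points (random spacing) and 4–21 points (regular spacing) at 24–52 weeks, falling to 0–8 and 2–20 at 260 weeks, depend on the assumed share, 2-unit transfusions and no drug effect. They show that the difference can matter; they do not predict it.

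This should be corrected before database lock. With no hypothesis test, it affects the meaning and level of a reported secondary rate, not error control or the primary safety objective.

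**What to change.** - In SAP 5.8.2.2, make the secondary endpoint analysis the RBC-TI rate with its exact 95% CI in HTB patients, as defined in 5.1.
- Keep the at-least-2-unit set as a labelled supplementary analysis, shown separately for 2–3 units and at least 4 units.
- Add a row to SAP 5.13 stating the added population and the reason for it.
- Time to and duration of RBC-TI may stay in the wider set if labelled so, preferably also shown for HTB. The RBC-TI regression models in 5.8.4 and the FACT-An association in 5.8.3.1 inherit the same definition and should carry the same label.

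The cost is SAP wording, one table and one row, with no new data. The HTB interval is modestly wider, as in the worked example. The change removes only the excess due to the denominator; chance responses from searching any 8-week window remain.
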